#### 11.9 Administration of IMP(s), placebo(s), and NIMP(s)

The IMP is intended for use under the guidance of a healthcare professional. After proper training in subcutaneous injection technique, a patient may self-inject the IMP if the nurse or clinician determines that it is appropriate.

After removing the pre-filled syringe from the refrigerator, the pre-filled syringe should be allowed to reach room temperature by waiting 30 minutes, before injecting. The syringe should not be shaken.

The total content (1 mL) of the pre-filled syringe should be administered as a subcutaneous injection only. Injection sites should be rotated, and injections should never be given into areas where the skin is tender, bruised, red, or hard.

#### 11.10 Destruction, return, and recall of IMP(s) and placebo(s)

All IMP that is to be destroyed will be documented and accounted for in accountability/drug destruction logs. This will be delegated to the local site pharmacy. Destruction of the study drug will be as per local requirements and will be authorised by the 3TR-PARTNER-RA Coordinating Office.

The batch number of all IMP supplies will be recorded on the accountability log and recall by IMP suppliers will be managed by the Sponsor.

Disposition of unused study drug not dispensed to patients, or partially used/returned study drug will be recorded as described in the IMP manual. IMP destruction of product not dispensed/administered must be confirmed with and approved by the 3TR-PARTNER-RA trials office.

#### 11.11 Dosage schedules

Abatacept (ORENCIA) should be administered weekly at a dose of 125 mg by subcutaneous (SC) injection.

If a patient misses an injection of Abatacept and is within three days of the planned date, he/she should be instructed to take the missed dose immediately and remain on the original weekly schedule. If the dose is missed by more than three days, the patient should be instructed when to take the next dose based on medical judgment (condition of the patient, status of disease activity, etc).

All doses including missed doses should be documented on the patient diaries and transcribed to the eCRF.

#### **11.12 Dosage modifications and delays**

Adherence to the planned dose regimen of study medication is required unless an adjustment is necessary for safety events as per applicable SmPC. All dosage modifications or interruptions should be clearly documented on the eCRFs.

#### **11.13 Management of Abatacept specific adverse events**

The clinical team should refer to the relevant current SmPC.

#### 11.14 Known drug reactions and interventions with other therapies

The clinical team should refer to the relevant current SmPC for known drug reactions and interactions.

#### 11.15 Concomitant medications

#### 11.15.1 DMARDs

Patient will not be allowed to take any other conventional, biologic or synthetic DMARDs during the trial.

#### 11.15.2 Non-steroidal anti-inflammatory drugs

The patient will be permitted to be on NSAIDs at any time throughout the duration of the study.

#### 11.15.3 Steroids

Nasal, cream or oral inhaled steroid preparations may be used throughout the study duration. Patients may receive corticosteroids throughout the trial at the discretion of the treating clinician. If steroids are clinically indicated, they should be tapered as rapidly as clinically feasible, in line with EULAR recommendations.

However, within 4 weeks prior to visit 1 (screening), visit 2 (biopsy/baseline), visit 5 (12 weeks), and visit 6 (16 weeks) the corticosteroid dose should not be increased and should not exceed prednisolone 10mg/day (or equivalent).

Intra-articular and other parenteral corticosteroids should not be used in the 4 weeks prior to visit 1 (screening), visit 2 (biopsy/baseline), visit 5 (12 weeks), and visit 6 (16 weeks). Patients may receive corticosteroids (po, intra-articular, or parenteral), if required, at the end of that study visit.

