# 7.0 Study Schedule

7.1 Schedule of treatment for each visit

# 7.2 Schedule of assessment (in diagrammatic format)

Visit number	1	2 (m)	3	4	5	6	7	Post treatment visit/call
Timeline (weeks)	-6 to -1	-3 to -1	0	4	8	12	16	30 or more days after visit 7
Deviation window (days from scheduled visit)		N/A		+/- 7 days	+/- 7 days	+/- 7 days	+/- 7 days	N/A
Visit type	Screening	Biopsy & Randomisation (m)	Baseline	Treatment Phase				Follow up
ENROLLMENT PROCEDURES								
Informed Consent	Х							
Inclusion and Exclusion Criteria	х							
Demographics	Х							
Medical History (f)	Х							
MEDICAL PROCEDURES								
Concomitant Medication review	x	Х	x	x	x	x	x	
RF & CCP (a)	Х							

ACR Criteria	X							
Pregnancy test (k)	Х		Х	Х	Х	Х	Х	
Chest X-ray (j)	Х							
ECG	Х							
Hepatitis serology, HIV, IGRA (i)	x							
Physical Examination	Х		Х	Х	Х	Х	Х	
Cardiovascular risk profile	Х							
Weight and Height	Х		Х	Х	Х	Х	Х	
Vital Signs (BP, pulse, temp.)	х		х	х	х	х	x	
Haematology, biochemistry panel, ESR, CRP (b)(c)	х		х	х	х	х	x	
DISEASE ACTIVITY ANALYSIS								
Joint Assessment (66/68) (I)	X		X	Х	Х	Х	Х	
X-ray Hands & Feet (h)			X				X	
CDAI	X		X	Х	Х	Х	Х	
DAS28	X		X	Х	Х	Х	Х	
VAS Pain Score	X		X	Х	Х	Х	Х	
HAQ Questionnaire			Х	Х	Х	Х	Х	
TREATMENT PROCEDURES								
Randomisation (g)		Х						
Commencement of randomised treatment			x					
Dispensing of randomised treatment			x	x	х	х		
Adverse Events		Х	Х	Х	Х	Х	Х	Х

Study Bloods	X		Х	Х	Х	Х	
Ultrasound (d)	X (d)					X (d)	
Pre-biopsy Assessment	Х					X (e)	
Synovial Biopsy (e)	X					X (e)	
Post-biopsy Assessment		Х					X (e)
Stool collection (optional)	Х		Х			X	
Urine collection (optional)	X		Х			Х	
Saliva collection (optional)	Х		Х			X	
PATIENT REPORTED OUTCOMES							
FACIT-fatigue Questionnaire		x	x		x	x	
SF-36		Х	Х		Х	Х	
Epworth Sleepiness scale		Х	Х		Х	Х	
EQ-5D-5L		Х	Х		Х	Х	

a. RF/CCP tests should be performed unless these tests have been done previously and do not need repeating as per local guidelines

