- j. A chest X-ray must be performed as screening for tuberculosis prior to biological therapy. A chest x-ray must be done at the screening visit to confirm the patient's eligibility unless a chest X-ray has been done in the preceding 3 months of the screening visit and the patient must not have had any pulmonary symptoms since then. The total protocol dose is less than 0.03mSv. This is equivalent to a few days of average natural background radiation in the UK.
- k. A pregnancy test will be performed at each study visit for female patients of childbearing age irrespective of the use of contraceptive methods.
- I. Joint assessments and VAS physician assessments to be completed by the nominated 'blinded joint assessor'. Joint assessments and VAS physician assessment are only required to be completed by the blinded joint assessor from the baseline visit onwards.
- m. Visit 2 (biopsy visit) may be combined with the completion of visit 1 (study screening visit) if all screening procedures and results are available prior to the biopsy, and the patient is confirmed eligible for enrolment into the study. Sites should contact the coordinating office before arranging.

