#### 7.5.1 Screening procedures (visit 1)

During the screening visit, written informed consent will be obtained from all patients by the Principal investigator or his/her designee before any protocol-specific procedure is performed. Study details, risks and benefits will all be reviewed and patients will be encouraged to ask questions and clarify any concerns. Demographic data (including age, assigned sex at birth and race) and medical history will be obtained. Patients, both men and women, will be reminded to use an acceptable and effective method of contraception during the study period and the appropriate time period after stopping study treatment. Patients may be screened up to 6 weeks prior to baseline visit. As per the study visit schedule screening will entail evaluation of:

- Inclusion and exclusion criteria
- Demographic data including age, assigned sex at birth, and race
- 2010 ACR/EULAR RA classification criteria
- Systemic disease assessment (RA involvement)
- Medical history
- Procedures history
- Allergies
- Concomitant medication
- DMARD therapy
- Corticosteroid therapy
- Clinical examination
- Rheumatoid Factor (RF) and Anti-CCP antibodies (CCP)a
- Routine blood tests (ESR, CRP, Full blood count (Haemoglobin, Red Cell Count,

- Haematocrit, White Blood Counts + differential including lymphocytes and
- neutrophils, Platelet count) liver function tests (ALT, AST), Kidney function/U&E (urea, sodium, potassium, creatinine, eGFR)b
- Total cholesterol, HDL, LDL, and triglycerides
- Hepatitis serology, HIV and IGRAc
- Vital signs
- Chest X-rayd
- ECG
- Pregnancy teste
- Joint assessment
- ACR-core set measures
- DAS 28 assessment
- Clinical Disease Activity Index (CDAI)
- VAS Pain score
- US assessmentf

Note: Anti-TNF therapy screening to include TB screening (IGRA), screening for Hepatitis and HIV according to local guidelines.

a RF/CCP tests should be performed unless these tests have been done previously and do not need repeating as per local guidelines.

b Routine blood tests do not need to be taken if the patient has already had these performed within 3 weeks of the screening visit

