#### 7.5.2 Biopsy visit and randomisation (visit 2)

All Patients in the main study will receive a synovial biopsy (refer to 3TR Synovial Biopsy SOP) between 1 to 3 weeks prior to their baseline visit. Patients will have the following assessments recorded prior to the synovial biopsy at this visit:

- Concomitant medication
- DMARD therapy
- Corticosteroid therapy
- Routine blood tests (ESR, CRP, Full blood count (Haemoglobin, Red Cell Count, Haematocrit, White Blood Counts + differential – including lymphocytes and neutrophils, Platelet count) liver function tests (ALT, AST), Kidney function/U&E (urea, sodium, potassium, creatinine, eGFR)a
- Study specific bloods
- Vital signs
- Pregnancy test in female patients of child bearing potential b
- Joint assessment c
- DAS 28
- CDAI
- ACR-core set measures
- VAS Pain Score
- Pre Biopsy Assessment Form
- Adverse events
- Ultrasound examination of the patients' joints prior to the synovial biopsy
- Pre-baseline synovial biopsy d
- Randomisatione

a Routine blood tests do not need to be taken if the patient has already had routine blood tests performed within 3 weeks of the biopsy visit.

b A pregnancy test will be performed at each study visit for female patients of child-bearing age irrespective of the use of contraceptive methods

c Joint assessments and VAS physician assessment are only required to be completed by the blinded joint assessor from the baseline visit onwards. If possible, the same assessor should perform the joint count at all (pre- and post-randomisation) visits from baseline to ensure consistency.

d A synovial biopsy prior to baseline is mandatory for patients in the main study as part of the patient stratification process.

e Randomisation see section 7.4

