#### 7.5.3 Biopsy visit and randomisation (visit 3)

Patients will receive Abatacept or placebo at their baseline visit depending upon randomisation and/or the treatment allocation algorithm. All assessments should be performed prior to the commencement of therapy. Patients at baseline will have the following assessments:

- Concomitant Medication
- DMARD therapy
- Corticosteroid therapy

- Clinical examination
- Cardiovascular risk assessment
- Routine blood tests (ESR, CRP, Full blood count (Haemoglobin, Red Cell Count, Haematocrit, White Blood Counts + differential – including lymphocytes and neutrophils, Platelet count) liver function tests (ALT, AST), Kidney function/U&E (urea, sodium, potassium, creatinine, eGFR)
- Vital signs
- Pregnancy test in women of childbearing potential a
- Joint assessment
- ACR core set measures
- Disease activity core data set (DAS28)
- Clinical Disease Activity Index (CDAI)
- VAS Pain score
- Physical function using the Health Assessment Questionnaire (HAQ)
- SF-36v2© (Licenced by Quality Metric Incorporated)
- FACIT Fatigue Questionnaire
- EQ-5D-5L
- Post Biopsy Assessment Form
- Adverse events
- Plain X-rays of hands and feet b
- Ultrasound assessment
- Optional urine, stool and saliva samples

All baseline assessments should be done within a +/- 7 day window

a A pregnancy test will be performed at each study visit for female patients of child bearing age irrespective of the use of contraceptive methods

b Plain X-rays of hands and feet do not need to be redone if the patient has already had them within 8 weeks of the baseline visit.

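### The steroid restriction in Section 11.15.3 misnumbers the week-12 and week-16 visits, so a site that follows the visit numbers has no limit before the primary CDAI

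*Protocol*

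**What the plan says.** Section 11.15.3 leaves steroids to the treating clinician, with advice to taper quickly, and then sets limits in the 4 weeks before certain visits. Three of its sentences matter here.

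- **Oral dose** (no increase, and no more than 10 mg/day prednisolone or equivalent). After screening, the visits are given as "visit 2 (biopsy/baseline), visit 5 (12 weeks), and visit 6 (16 weeks) the corticosteroid dose should not be increased".
- **Injected steroids.** "Intra-articular and other parenteral corticosteroids should not be used in the 4 weeks prior to visit 1 (screening), visit 2 (biopsy/baseline"; the list then ends with the same visit 5 and visit 6 pairings.
- **Allowance.** "Patients may receive corticosteroids (po, intra-articular, or parenteral), if required, at the end of that study visit".

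The schedule in Section 7.2 numbers the visits differently: screening is visit 1, biopsy visit 2, week 0 visit 3, and weeks 4, 8, 12 and 16 are visits 4 to 7. Its last column, the post-treatment contact, is timed at "30 or more days after visit 7". Section 7.5.4 (visits every 4 weeks, ±7 days, from baseline) and Section 8.2 both call week 16 visit 7.

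On the pre-treatment side, Section 7.5.2 places the biopsy "between 1 to 3 weeks prior to their baseline visit", and Section 7.5.3 covers visit 3: "Patients will receive Abatacept or placebo at their baseline visit".

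**The concern.** The primary endpoint is the change in CDAI at 16 weeks. CDAI is the sum of tender and swollen joint counts and the patient and physician global scores (Section 7.6.4), all of which steroids can lower directly. The restriction is there to keep recent steroid changes out of that measurement.

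Each sentence identifies a visit in two ways, by number and by week, and for the two follow-up visits these disagree. A site that goes by the week protects the 4 weeks before the primary assessment. A site that goes by the number protects the 4 weeks before week 12 instead, and nothing limits steroids after that. Two sites could both say that they complied while applying different rules in the weeks that matter most. Analysis cannot undo a steroid already given, so the text that binds sites has to be right.

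**Working it through.** **1. Visit-to-week pairing.** The section's own pairing is the figure to check. Section 7.2 has visit 3 at week 0 and Section 7.5.4 spaces visits 4 to 7 by 4 weeks, so the scheduled day of visit v is 28 × (v − 3).

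| Visit | Scheduled day | Week | Section 11.15.3 says |
|---|---|---|---|
| 5 | 28 × 2 = 56 | 8 | 12 weeks |
| 6 | 28 × 3 = 84 | 12 | 16 weeks |
| 7 | 28 × 4 = 112 | 16 | not listed |

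The section's pairing does not reproduce. Both follow-up numbers are one too low, in both sentences.

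**2. What each reading restricts, on the planned schedule.**

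| Reading | Restricted days | Days 84 to 112 |
|---|---|---|
| By week label | 56–84 and 84–112 | restricted |
| By visit number | 28–56 and 56–84 | no limit |

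The readings agree only on days 56 to 84.

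**3. Length of the unprotected interval with visit windows.** Visit 6 may fall on days 84 ± 7 = 77 to 91, and visit 7 on days 112 ± 7 = 105 to 119.

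- Shortest gap: 105 − 91 = 14 days.
- Planned gap: 112 − 84 = 28 days.
- Longest gap: 119 − 77 = 42 days.

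Read by number, the whole gap has no limit, and the allowance sentence would expressly permit steroids at its start.

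**4. The end-of-visit allowance once the numbers are right.** Week 12 is a listed visit, so one reading lets steroids start at its end. On schedule that is 28 days before week 16, on the boundary of the restricted window. It is clearly inside the window only when visits 6 and 7 are less than 28 days apart (14 to 27 days), or when an oral course above 10 mg/day started then continues. The text does not say which sentence prevails.

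The same question arises between screening and biopsy. Section 7.5.1 says "Patients may be screened up to 6 weeks prior to baseline visit", and a footnote to Section 7.2 says "Visit 2 (biopsy visit) may be combined with the completion of visit 1 (study screening visit"). With visit 1 on days −42 to −7 and visit 2 on days −21 to −7, the gap runs from 0 to −7 − (−42) = 35 days. It exceeds 28 days only if screening is before day −35 and biopsy after day −14.

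**5. The biopsy/baseline label.** Visit 2 precedes visit 3 by 7 to 21 days. If the label means the biopsy visit alone, a steroid given at its end is allowed 7 to 21 days before the week-0 CDAI. If it also covers visit 3, the 4-week window spans that whole interval and the allowance after biopsy could not be used. The text does not settle which is meant.

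**The case against.** The strongest reply is that the error corrects itself. Each wrong number is printed next to its week, and the protocol consistently places the primary assessment at week 16. To leave days 84 to 112 open, a site would have to disregard the printed week. This stands as far as likely intent goes. A reader might infer that there is no steroid limit before the primary endpoint; the week labels do not support that. But the schedule is organised by visit number, and no other text tells a site which identifier to follow.

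A reader might also count the biopsy/baseline label as a third misnumbering. The documents do not support that. Sections 7.6.16, 8.2 and 9.5.2 loosely call the visit 2 biopsy the baseline biopsy, so the number 2 may well be right and the label merely unclear.

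Nor does the allowance plainly contradict the restriction. The singular wording can be taken to mean only the last-named visit, or to mean that a visit's own restriction ends when its assessments are done while the bar before the next listed visit continues. On either reading there is no conflict. The 14-day figure also needs visit 6 a week late and visit 7 a week early. What remains is a request for clarification.

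Finally, no harm is quantified. Section 7.3 keeps the biopsy result from site staff, Section 7.4 keeps the treatment from them, and concomitant medication is reviewed at visits 1 to 7. That limits the consequence but does not decide which rule applies between weeks 12 and 16.

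**Conclusion.** The numbering error for weeks 12 and 16 is established: it appears in both restriction sentences and conflicts with Section 7.2, and for week 16 also with Sections 7.5.4 and 8.2. Its size is the interval that a site following the numbers would leave open before the primary CDAI: 28 days as planned, 14 to 42 days within the visit windows. This assumes that the schedule is right and Section 11.15.3 wrong, which the agreement of the other sections supports.

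The baseline label and the end-of-visit allowance are secondary points, unclear rather than wrong.

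A reader might go further and infer bias between Group 1 and Group 3, or a loss of power. The documents give no steroid-use rate, no steroid effect on CDAI and no reason to expect different use in the two biomarker groups, so neither is claimed. This should be fixed because it concerns an operative rule just before the primary measurement and the correction is nearly free.

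**What to change.** In both restriction sentences of Section 11.15.3, change the follow-up visits to *visit 6 (12 weeks)* and *visit 7 (16 weeks)*, and send sites a clarification memo. The cost is a small protocol amendment with its approvals. No visits, data or analyses change, and a stable dose up to 10 mg/day stays allowed.

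In the same amendment the sponsor should settle two points:

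- **Baseline.** State whether the visit 2 label means the biopsy visit only. If visit 3 is also restricted, list it separately; if not, say that steroids between biopsy and baseline are permitted.
- **Allowance.** If that is the intent, state that it does not override the 4-week restriction before week 16. A general exception tied to the 4 weeks before any other listed visit would be hard to apply, because the visit 7 date is not yet fixed at week 12. It would also largely remove the allowance after both screening and week 12. Limiting relief for patients who flare is a clinical trade-off for the sponsor to make openly; the renumbering need not wait for it.

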#### 11.15.4 Other medications

Other medications (with the exception of investigational / unlicensed drugs) are permitted as clinically required during the study and should be recorded on the applicable visit Case Report Form (CRF).

#### 11.16 Management of overdose

Any overdoses should be managed as per section 4.9 of the relevant current SmPC.

#### **11.17 Precautions regarding contraception**

Abatacept is not recommended for use during pregnancy unless the clinical condition of the woman requires treatment with abatacept. Women of childbearing potential must agree to use effective contraception during treatment and up to 14 weeks after the last dose of abatacept in order to participate in this trial. Pregnant patients will be excluded from this trial and any participant who becomes pregnant during their participation in the trial, will be withdrawn immediately when the study team are notified of pregnancy from trial treatment. Men with partners of childbearing potential will be reminded to use an acceptable and effective method of contraception during the study period and the appropriate time period after stopping study treatment (up to 14 weeks after the last dose of abatacept).

If a participant's partner becomes pregnant whilst or after (up to 14 weeks after the last dose of abatacept) the partner is participating in the trial, pregnant partner will be asked to consent for the clinical team to collect information about their health and their pregnancy. This is optional and if pregnant partner agrees, clinical team will contact them after they have given birth to your baby asking you about their pregnancy and delivery and the health of their baby. If a participant's partner becomes pregnant whilst the male partner is participating, participant will continue the treatment.

Pregnancy should be reported via a paper form and should be sent to [contact] that will notify and report to the Sponsor (see section 12.9)

#### 11.18 Arrangements for post-study access to IMP and care

Participants will not have access to the study intervention after the end of their participation and may return to the standard of care received prior to entering the study, at the discretion of their usual physician.

## 12.0 Pharmacovigilance

#### **12.1 General definitions**

Term	Definition
Adverse Event (AE)	Any untoward medical occurrence in a participant to whom a medicinal product has been administered, including occurrences which are not necessarily caused by or related to that product.
Adverse Reaction (AR)	An untoward and unintended response in a participant to an investigational medicinal product which is related to any dose administered to that participant. The phrase " response to an investigational medicinal product " means that a causal relationship between a study medication and an AE is at least a reasonable possibility, i.e. the relationship cannot be ruled out. All cases judged by either the reporting medically qualified professional or the sponsor as having a reasonable suspected causal relationship to the study medication qualify as adverse reactions.
Serious Adverse Event (SAE)	
 
A serious adverse event is any untoward medical occurrence that:
 
Results in death.
 
Is life-threatening.
 
Requires inpatient hospitalisation or prolongation of existing hospitalisation (excludes day cases)
 
Results in persistent or significant disability/incapacity.
 
Consists of a congenital anomaly or birth defect.
 
Other 'important medical events' may also be considered serious if they jeopardise the participant or require an intervention to prevent one of the above consequences.
 
NOTE: The term "life-threatening" in the definition of "serious" refers to an event in which the participant was at risk of death at the time of the event; it does not refer to an event which hypothetically might have caused death if it were more severe.
 

Serious Adverse Reaction (SAR)	An adverse event that is both serious and, in the opinion of the reporting Investigator or medical assessor, believed with reasonable probability to be due to one of the study treatments, based on the information provided.
Suspected Unexpected Serious Adverse Reaction (SUSAR)	
 
A serious adverse reaction, the nature and severity of which is not consistent with the information about the medicinal product in question set out in the Reference Safety Information (RSI):
 
In the case of a product with a marketing authorisation, in the summary of product characteristics (SmPC) for that product.
 
In the case of any other investigational medicinal product, in the investigator's brochure (IB) relating to the study in question.
 

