#### Table 5.4.1-1: Adverse Events Summary During the Double-blind, Placebo-Controlled Period, All Treated Subjects

 Deaths	Abatacept (N=2653)		Placebo (№=1485)		Total (N=4138)	
	12	( 0.5%)	12	( 0.8%)	24	( 0.6%)
SAEs	331	(12.5%)	174	(11.7 <del>%</del> )	505	(12.2%)
Related SAEs	75	( 2.8%)	30	( 2.0%)	105	( 2.5%)
Discontinued due to SAEs	68	( 2.6%)	22	( 1.5%)	90	( 2.2%)
AEs	2334	(88.0%)	1258	(84.7%)	3592	(86.8%)
Related AEs	1311	(49.4%)	680	(45.8%)	1991	(48.1%)
Discontinued due to AEs	138	( 5.2%)	55	( 3.7%)	193	( 4.7%)
Infections	1440	( 54.3%)	767	( 51.6%)	2207	7 ( 53.3% )
Malignancies	31	( 1.2 <del>%</del> )	14	( 0.9%)	45	( 1.1%)
Autoimmune AEs	198	(7.5%)	115	5 (7.7%)	31	3 (7.6%)

Includes data up to 56 days or 60 (Phase 2 IV) post last dose in the short-term double-blind period or start of the long-term period whichever occurred first.

Adverse events related to study drug are those with a certain, probable, possible, related or a missing relationship to study drug. Studies Included: IM101226, IM101063, IM101023, IM101043, IM101031, IM101029, IM101102,

IMIOIIOI, IMIOIIOO MEDDRA VERSION: 19.0

Table 1: AE Summary from Investigator's Brochure v26.0 22-Dec-2022

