#### Causality

Assessing the causality of all serious adverse events/reactions in relation to the study treatment according to the definition given. If the SAE is assessed as having a reasonable causal relationship, then it is defined as a SAR.

• Expectedness

Assessing the expectedness of all SARs according to the definition given. If the SAR is unexpected (as per the RSI), then it is a SUSAR.

• Severity

Assessing the severity of the event according to the following terms and assessments. The intensity of an event should not be confused with the term "serious" which is a regulatory definition based on participant/event endpoint criteria.

- **Mild**: Some discomfort noted but without disruption of daily life
- Moderate: Discomfort enough to affect/reduce normal activity
- Severe: Complete inability to perform daily activities and lead a normal life

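### Section 12.1 sets a stricter causality wording for a serious adverse reaction than for an adverse reaction, so an unexpected serious event rated only possibly related can miss SUSAR status

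*Protocol*

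**What the plan says.** The definitions table in Protocol section 12.1 treats an event as an AR when "a causal relationship between a study medication and an AE is at least a reasonable possibility, i.e. the relationship cannot be ruled out". It adds that cases judged by the reporting clinician or by the sponsor "as having a reasonable suspected causal relationship to the study medication qualify as adverse reactions".

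The SAR row of the same table does not build on the AR row. It asks that the event be serious and, in the opinion of the reporting investigator or the medical assessor, "believed with reasonable probability to be due to one of the study treatments". The SUSAR row then starts from the SAR: "A serious adverse reaction, the nature and severity of which is not consistent with the information about the medicinal product in question".

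Section 12.2 gives the site its working rule: "If the SAE is assessed as having a reasonable causal relationship, then it is defined as a SAR". On expectedness it says: "If the SAR is unexpected (as per the RSI), then it is a SUSAR". The causality item in 12.2 also tells the investigator to assess according to the definition given, which leads back to 12.1.

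**The concern.** A SAR should be an AR that is also serious. In section 12.1 it is not, because the causality test tightens from possibility to probability when the event becomes serious. The stricter wording therefore sits on the category where a missed classification matters most.

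Two things are at stake. First, section 12.6.2 attaches unblinded reporting to the MHRA to SUSAR status, so an event that does not reach SAR cannot enter that route under the 12.1 wording. Secondly, the trial is international with at least 10 centres (section 14.2). If one site works from the table and another from section 12.2, the same kind of event can be classified differently, and the SUSAR summary by treatment and pathotype in section 14.9 carries that inconsistency.

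**Working it through.** The point is textual and the plan states no figure to reproduce. The check is to take one event through each rule. Suppose an event is serious, is unexpected against the reference safety information, and has a causal link that the assessor cannot exclude but does not think probable.

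1. **AR row, 12.1.** The test is possibility. The event is an AR.
2. **SAE row, 12.1.** There is no causality test. The event is an SAE.
3. **SAR row, 12.1.** The test is probability. The event is not a SAR, although it is both an AR and serious.
4. **SUSAR row, 12.1.** The event must first be a SAR. It is not a SUSAR, although it is unexpected.
5. **Section 12.2, by its own words.** The test is a reasonable causal relationship, close to the second sentence of the AR row and with no mention of probability. The event can be a SAR and, being unexpected, a SUSAR.
6. **Section 12.2, by its pointer to the definition given.** For a serious event the natural definition to consult is the SAR row. That returns the result of steps 3 and 4.
7. **Section 7.4.** The sponsor's right to break the code covers unexpected SAEs suspected of being caused by the product. Suspicion matches the AR row, and the event is covered.

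Steps 3 and 4 disagree with steps 5 and 7, and step 6 leaves section 12.2 open to either reading.

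The next question is what depends on the class:

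- **Depends on it:** unblinded SUSAR reporting to the MHRA (12.6.2) and the SUSAR summary (14.9).
- **Does not depend on it:** SAE reports to the sponsor within 24 hours (12.6), SAE reports to the manufacturer whether related or not (12.6.1), and the chief investigator's review of every SAE within 72 hours (12.7).

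**The case against.** The strongest defence is that section 12.2 is the rule sites apply, that it contains no probability test, and that section 7.4 also speaks of suspicion. On that reading the possibly related event is classified correctly. Every SAE is in any case collected without a causality filter and reviewed for relatedness by the chief investigator, who cannot downgrade the site's causality assessment.

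Most of this stands, and it limits the point. It does not remove it. Section 12.2 sends the assessor back to the definitions. The chief investigator's review comes under the same SAR row, which names the medical assessor. The bar on downgrading does not help when the site has already applied the stricter wording.

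A reader might infer more than the documents support:

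- **That such events are always excluded, or lost.** Section 12.2 permits the wider reading, and all SAEs are reported regardless of causality.
- **That the sponsor's code-break right in 7.4 or the DSUR is cut back.** The first is worded by suspicion. The second (13.1) rests on a risk-benefit review of all events in the study. Neither is tied to the SAR class.
- **That the trial's related-SAE rate would not compare with the background safety table**, whose footnote reads "Adverse events related to study drug are those with a certain, probable, possible, related or a missing relationship to study drug". The footnote does count possible relationships as related, but the protocol plans no comparison with that table. Its exploratory endpoint is SAEs from 0 to 16 weeks (2.4).
- **That a number of missed reports can be given.** The documents state neither the share of serious events rated only possible nor the share that would be unexpected.

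**Conclusion.** The inconsistency is real and the protocol is wrong as written: section 12.1 applies two thresholds to one judgement, and SUSAR inherits the stricter one. The exposure is misclassification of SAR and SUSAR status for serious, unexpected events rated possibly but not probably related. The result could be a missed expedited report to the regulator or uneven classification between sites.

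This rests on one assumption, that some assessors will apply the SAR row literally or follow the pointer in section 12.2 to it. The size cannot be expressed as a count from the documents. The point does not touch the primary endpoint, the power calculation or any efficacy analysis. It is a small correction to a rule that decides regulatory reporting, and a missed expedited report cannot be put right at analysis.

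**What to change.** In section 12.1, define a SAR as any AR, by the causality wording of the AR row and as judged by the investigator or the sponsor's assessor, that also meets one of the listed seriousness criteria. Repeat that causality wording in section 12.2 in place of the present phrase. The SUSAR row can then stay as it is, and AR, SAR and SUSAR will share one threshold that agrees with the suspicion wording in section 7.4. Because the SAR row refers to study treatments and the AR row to the investigational product, the revised text should also state which products are meant.

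The cost is a change of wording in two sections, carried through to the SAE form and site training where they repeat the definitions, and possibly an occasional extra expedited report. No design element or sample size changes.
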